## 8. Safety Analyses

389  
390 All enrolled participants will be included in these analyses and all their safety events up to the  
391 final 26-week visit will be reported. (Note: a separate Extension Study will start when a  
392 participant completes the randomized trial and its analyses will be detailed in a separate Protocol  
393 and Statistical Analysis Plan.)

394 The circumstances of all reportable cases of the following will be summarized and tabulated by  
395 treatment group:

- Severe hypoglycemia
- Diabetic ketoacidosis
- Ketone events defined as a calendar day with ketone level  $>1.0$  mmol/L
- CGM-measured hypoglycemic events ( $\geq 15$  minutes with glucose concentration  $<54$  mg/dL)
- CGM-measured hyperglycemic events ( $\geq 15$  minutes with glucose concentration  $>300$  mg/dL)
- BG-measured hypoglycemic events (one BG record  $<54$  mg/dL)
- BG-measured hyperglycemic events (one BG record  $>350$  mg/dL)
- Worsening of HbA1c from baseline to 26 weeks by  $>0.5\%$
- Serious adverse events with a possible or greater relationship to a study device (including anticipated and unanticipated adverse device effects)
- Other serious adverse events not related to a study device
- Adverse device effects (ADE) that do not meet criteria for SAE

410

411 For the following outcomes, mean  $\pm$  SD or summary statistics appropriate to the distribution will  
412 be tabulated by treatment group:

- 413 • Number of SH events and SH event rate per 100 person-years
- 414 • Number of DKA events and DKA event rate per 100 person-years
- 415 • Any adverse event rate per 100 person-years

416

417 If there are at least 10 events across both treatment arms, the numbers will be compared between  
418 the two treatment arms using a robust Poisson regression and the percentage of subjects with at  
419 least one event will be compared using logistic regression. The regression will adjust for the  
420 participant-reported number of events 12 months prior to the start of the study and site as random  
421 effect. The amount of follow up will be included as an offset covariate to compare the rates.

422 The analyses for the two continuous CGM-measured outcomes will parallel those mentioned  
423 above for the primary outcome.

424 For subjects participating in the Extension Study, the comparison of safety outcomes between the  
425 two treatment groups only include those events occurring on or after randomization until the 26  
426 week visit. For subjects not participating in the Extension Study or dropouts, the comparison of  
427 safety outcomes between the two treatment groups only include those events occurring on or  
428 after randomization.

429

430 Any pre-randomization adverse events will be tabulated separately.

431

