750 751	Participants will be instructed to download the study device prior to each phone visit or on at least every 4 week basis throughout the remainder of the study.
752	5.1.4 1-Week Phone Contact
753 754	Study staff will perform a phone call with the participant within 7 (± 1) days following randomization.
755	The following will occur:
756	Assessment of compliance with study device use by review of any available device data
757	• Assessment of adverse events, adverse device effects, and device issues
758	 Study staff will answer any questions related to device use
759 760	Participants will then complete an additional week of home use with the study system. Participants will return to clinic 14 (±3) days from the date of randomization.
761	5.1.5 2-Week Visit (Training Review and Insulin Pump Optimization)
762 763	The participant will be offered review training to address any questions on the use of the study device including meal bolus strategies and strategies related to pump use and exercise.

D981-FF58-4975-AEFF PAGE 34 OF 74

764	The following will occur:
765	• Assessment of compliance with study device use by review of any available device data
766	 Assessment of adverse events, adverse device effects, and device issues
767 768 769	• Study staff will answer any questions related to device use and follow the procedure for insulin pump optimization described in section 3.2 using the study CGM available data from the previous two weeks.
770 771	• The study blood glucose meter and study ketone meter will be downloaded and QC tested with at least two different concentrations of control solution if available.
772	5.2 Procedures for the SAP Group
773 774 775 776 777	Participants in the SAP group will use an insulin pump with no automated insulin delivery in conjunction with the study CGM, study blood glucose meter and study ketone meter. Participants not already using an insulin pump with no automated insulin delivery at enrollment will be provided with a study pump to use. Study pump training and/or study CGM training will be provided if the participant is initiating use of these devices at this point.
778 779 780	Participants may use available manufacturer-provided software and features of the study CGM related to mobile data access or remote monitoring, but will be instructed not to use any third-party components for this purpose.
781	5.2.1 Study Device Data Download

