Device Complaints and Malfunctions: A device complication or complaint is something that happens to a device or related to device performance, whereas an adverse event happens to a participant. A device complaint may occur independently from an AE, or along with an AE. An AE may occur without a device complaint or there may be an AE related to a device complaint. A device malfunction is any failure of a device to meet its performance specifications or otherwise perform as intended. Performance specifications include all claims made in the labeling for the device. The intended performance of a device refers to the intended use for which the device is labeled or marketed. (21 CFR 803.3). Note: for reporting purposes, sites will not be asked to distinguish between device complaints and malfunctions.

D981-FF58-4975-AEFF PAGE 45 OF 74

1075	8.1.2 Reportable Adverse Events
1076 1077	For this protocol, a reportable adverse event includes any untoward medical occurrence that meets one of the following criteria:
1078	1. A serious adverse event
1079 1080	2. An Adverse Device Effect as defined in section 8.1.1, unless excluded from reporting in section 8.2
1081	3. An Adverse Event occurring in association with a study procedure
1082	4. Hypoglycemia meeting the definition of severe hypoglycemia as defined below
1083 1084	5. Diabetic ketoacidosis (DKA) as defined below or in the absence of DKA, a hyperglycemic or ketosis event meeting the criteria defined below
1085 1086 1087	Hypoglycemia and hyperglycemia not meeting the criteria below will not be recorded as adverse events unless associated with an Adverse Device Effect. Skin reactions from sensor placement are only reportable if severe and/or required treatment.
1088	Pregnancy occurring during the study will be recorded.
1089	8.1.2.1 Hypoglycemic Events

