1121 1122 1123	The study investigator will assess the relationship of any adverse event to be related or unrelated by determining if there is a reasonable possibility that the adverse event may have been caused by the study device.
1124 1125	To ensure consistency of adverse event causality assessments, investigators should apply the following general guideline when determining whether an adverse event is related:
1126	Yes
1127 1128 1129 1130 1131 1132	There is a plausible temporal relationship between the onset of the adverse event and the study intervention, and the adverse event cannot be readily explained by the participant's clinical state, intercurrent illness, or concomitant therapies; and/or the adverse event follows a known pattern of response to the study intervention; and/or the adverse event abates or resolves upon discontinuation of the study intervention or dose reduction and, if applicable, reappears upon re-challenge.
1133	No
1134 1135 1136 1137	Evidence exists that the adverse event has an etiology other than the study intervention (e.g., preexisting medical condition, underlying disease, intercurrent illness, or concomitant medication); and/or the adverse event has no plausible temporal relationship to study intervention.
1138	8.1.4 Intensity of Adverse Event
1139 1140 1141 1142	The intensity of an adverse event will be rated on a three point scale: (1) mild, (2) moderate, or (3) severe. It is emphasized that the term severe is a measure of intensity: thus a severe adverse event is not necessarily serious. For example, itching for several days may be rated as severe, but may not be clinically serious.
1143 1144	• MILD: Usually transient, requires no special treatment, and does not interfere with the participant's daily activities.

D981-FF58-4975-AEFF PAGE 47 OF 74

- MODERATE: Usually causes a low level of inconvenience or concern to the participant and may interfere with daily activities, but is usually ameliorated by simple therapeutic measures.
- SEVERE: Interrupts a participant's usual daily activities and generally requires systemic drug therapy or other treatment.

1149	8.1.5 Coding of Adverse Events

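### SAP 8 tests the any-adverse-event rate between arms, but device-linked events are captured more broadly in the closed-loop arm, so the ratio mixes device effect with ascertainment

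*SAP*

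**What the plan says.** To avoid confusion with the plan itself, the sensor-augmented pump group is called the control arm below, and the closed-loop group CLC.

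**The comparison.** SAP 8 names three outcomes to summarize by arm: the number and rate of severe hypoglycemia (SH) events, the number and rate of DKA events, and "Any adverse event rate per 100 person-years". The next paragraph sets the trigger, "If there are at least 10 events across both treatment arms, the numbers will be compared between", and continues "the two treatment arms using a robust Poisson regression and the percentage of subjects with at", the percentage with an event being tested by logistic regression. The adjustment is for "participant-reported number of events 12 months prior to the start of the study and site as random" effect, with follow-up as an offset. Protocol 10.8 has the same list and comparison with a vaguer trigger. SAP 15 leaves safety p-values unadjusted for multiplicity.

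**What is recorded.** Protocol 8.1.2 admits an event by one of five routes: serious event, Adverse Device Effect, event linked to a study procedure, SH, or DKA or another hyperglycemia/ketosis event as defined in 8.1.2.2. The device route is worded "An Adverse Device Effect as defined in section 8.1.1, unless excluded from reporting in section 8.2". The section adds: "Hypoglycemia and hyperglycemia not meeting the criteria below will not be recorded as adverse events unless associated with an Adverse Device Effect". Under Protocol 8.1.3 an event counts as related "if there is a reasonable possibility that the adverse event may have been caused by the study device".

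**Who uses which device.** All CLC participants use the study pump with Control-IQ and the study CGM (Protocol 5.1.1). For the control arm, Protocol 5.2 says: "Participants not already using an insulin pump with no automated insulin delivery at enrollment will be provided with a study pump to use". Protocol 5.3.1.1 confirms that other participants stay on a personal pump. All control participants use the study CGM, glucose meter and ketone meter.

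**The concern.** The outcome's name suggests a count of all adverse events. It is a count of reportable ones, and for milder glycemic events attribution to a study device decides whether a record exists at all. The more study devices a participant uses, the more events can enter by that route.

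Take a non-severe hypoglycemia that follows automated insulin delivery in CLC. It can be recorded as an Adverse Device Effect. The same glucose excursion in a control participant dosing by a personal pump, with no study device implicated, is not recorded. The route is not hypothetical: item 4 of the SAP addendum describes a studywide suspension of the closed-loop feature over unneeded insulin delivery.

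A raised all-event rate ratio could then be read as harm when part of it is broader recording. Equally, a real reduction in events that both arms record alike could be masked in the total.

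**Working it through.** **1. Is the all-event rate tested?** The comparison sentence follows directly on the three-item list and excludes none of the items. On a natural reading all three go through the Poisson and logistic models.

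**2. Which routes depend on the study device?**

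| Route (Protocol 8.1.2) | Does attribution to a study device decide whether the event is recorded? |
|---|---|
| Serious adverse event | No |
| Study-procedure event | No |
| Severe hypoglycemia | No |
| DKA, hyperglycemia or ketosis meeting 8.1.2.2 | No, but one criterion (ketones at or above 1.0 mmol/L) also needs contact with a health care provider |
| Adverse Device Effect | Yes |

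The asymmetry lies in the last row. It is narrower than that row suggests, because the route excludes what Protocol 8.2 excludes. Infusion-set occlusion without ketosis and component disconnections are on that list, so they are not part of the problem.

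**3. Can the model correct it?** The covariate is a reported count of events in the previous 12 months. The baseline history in SAP 11 covers SH and DKA only. For the all-event outcome the listed data hold no such count, so the model cannot be fitted as written. Even if it could, a pre-study count would not adjust for differential recording after randomization.

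**4. Size.** The plan gives no adverse event rate, rate ratio or power to reproduce. Its one computed design figure, the minimum sample size, does reproduce: control n = 1.5 × [12 × (1.960 + 1.282) / 7.5]² = 40.35, rounded up to 41, with 82 CLC, total 123.

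Inputs for the illustration:
- From the documents: 168 randomized 2:1, hence 112 and 56; six months each, hence 112 × 0.5 = 56 and 56 × 0.5 = 28 person-years.
- Assumed: arm-neutral rate L of 20 or 40 per 100 person-years, equal in both arms; device-linked rate D of 10, 20 or 40 in CLC; share f of D that is also recorded in the control arm.

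Apparent rate ratio = (L + D) / (L + f × D). For L = 20, D = 20, f = 0.5 this is 40/30 = 1.33. Each cell gives the ratio and, in brackets, the probability of two-sided p < 0.05 from an exact conditional binomial test on Poisson counts, given at least 10 events.

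| L | D | f = 1 (equal capture) | f = 0.5 | f = 0 (none) |
|---|---|---|---|---|
| 20 | 10 | 1.00 (0.04) | 1.20 (0.05) | 1.50 (0.10) |
| 20 | 20 | 1.00 (0.04) | 1.33 (0.08) | 2.00 (0.28) |
| 20 | 40 | 1.00 (0.04) | 1.50 (0.18) | 3.00 (0.75) |
| 40 | 10 | 1.00 (0.04) | 1.11 (0.05) | 1.25 (0.07) |
| 40 | 20 | 1.00 (0.04) | 1.20 (0.07) | 1.50 (0.18) |
| 40 | 40 | 1.00 (0.04) | 1.33 (0.15) | 2.00 (0.56) |

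The trigger would be met: at L = D = 20, expected events are 22.4 in CLC plus 5.6 (f = 0) to 11.2 (f = 1) in control, or 28.0 to 33.6 in all. The exact test ignores overdispersion. A gamma-Poisson simulation (shape 1, robust variance, 4,000 trials per setting) at f = 0 gave median ratios of 1.3 to 3.1 and rejection in 8% to 68% of trials, so the picture is similar.

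A value of f below 1 can arise because control-arm events go unrecorded or because they do not occur. The ratio is the same either way, which is why one number cannot be interpreted.

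**The case against.** A fair defence has five parts.

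- *The rules do not mention arm.* Correct. Every control participant uses a study CGM and meters, and some use a study pump; Protocol 2.1 aims for at least 30 completers who enter on injections. A reader might infer that device-linked events are recorded only, or almost only, in CLC. The documents do not support that. Zero control-arm capture is a limit, not an expectation.
- *An excess in CLC may be real.* Also correct. An adverse effect of automated delivery that cannot occur in the control arm is a genuine consequence of assignment. A reader might infer that the comparison is biased whatever the true safety difference, so that any excess is artefact. That does not follow. What follows is that the total cannot separate the two sources.
- *The test may not be intended.* The list gives counts for SH and DKA but only a rate for all events, and the covariate does not exist for the latter. This makes the intention doubtful, but the text as written still includes the outcome and needs editing on this ground too.
- *The components are already tabulated.* SAP 8 separately shows SH, DKA, serious events by relatedness, and non-serious Adverse Device Effects, so a reader can decompose the total. This limits the harm and makes the change cheap; it does not make the tested ratio interpretable.
- *Little hangs on it.* It is an unadjusted safety p-value outside the primary and hierarchical tests, and broader capture works against the investigational device. That limits the weight of the point.

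**Conclusion.** The point holds in a limited form. On the literal text SAP 8 tests an all-event rate whose ascertainment is broader in CLC, because milder glycemic events are recorded only through attribution to a study device and some control participants remain on a personal pump. The planned covariate cannot repair this and is not available for the outcome.

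The direction of the ascertainment difference follows from the documents; its size does not. Under the assumed rates the apparent ratio is 1.0 with equal capture, 1.11 to 1.50 with half capture, and 1.25 to 3.00 with none, the last being an upper bound. The chance of p < 0.05 stays near 0.04 with equal capture, is 0.05 to 0.18 with half, and is 0.07 to 0.75 with none. All of this rests on assumed rates, equal arm-neutral rates and full six-month follow-up.

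**What to change.** In SAP 8, by a short addendum:

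1. Limit the formal between-arm comparison to SH, DKA, serious adverse events, and hyperglycemia/ketosis events meeting Protocol 8.1.2.2. Add a note to the last that its contact-based criterion depends on contact behaviour. Protocol 5.1.1 asks CLC participants to call staff about health and technical issues; Protocol 5.2 has no matching instruction for the control arm.
2. Use the prior-12-month covariate only for SH and DKA, where SAP 11 lists it.
3. Report Adverse Device Effects and the any-adverse-event total by arm as counts and rates without a test, labelled as differing in ascertainment between arms.

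The cost is a few lines of text and a flag on event categories that are largely tabulated already. No new data are needed. The one loss is a p-value for the all-event total.

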1215 1216 1217	Each principal investigator is responsible for reporting serious study-related adverse events and abiding by any other reporting requirements specific to his/her Institutional Review Board or Ethics Committee.
1218 1219 1220 1221	Upon receipt of a UADE report, the Sponsor will investigate the UADE and if indicated, report the results of the investigation to the sites' IRBs, and the FDA within 10 working days of the Sponsor becoming aware of the UADE per 21CFR 812.46(b) (2). The Medical Monitor must determine if the UADE presents an unreasonable risk to participants. If so, the Medical Monitor

D981-FF58-4975-AEFF PAGE 50 OF 74

1222 1223 1224	must ensure that all investigations, or parts of investigations presenting that risk, are terminated as soon as possible but no later than 5 working days after the Medical Monitor makes this determination and no later than 15 working days after first receipt notice of the UADE.
1225 1226 1227	In the case of a device system component malfunction (e.g. pump, CGM, control algorithm), information will be forwarded to the responsible company by the site personnel, to be handled by its complaint management system.
1228	8.5 Stopping Criteria
1229	8.5.1 Participant Discontinuation of Study Device
1230	Rules for discontinuing study device use are described below.
1231 1232 1233 1234	• The investigator believes it is unsafe for the participant to continue on the intervention. This could be due to the development of a new medical condition or worsening of an existing condition; or participant behavior contrary to the indications for use of the device that imposes on the participant's safety
1235	• The participant requests that the treatment be stopped
1236	Participant pregnancy
1237	Two distinct episodes of DKA
1238	• Two distinct severe hypoglycemia events as defined in section 8.1.2.1
1239 1240 1241	If pregnancy occurs, the participant will be discontinued from the study entirely. Otherwise, even if the study device system is discontinued, the participant will be encouraged to remain in the study through the final study visit.
1242	8.5.2 Criteria for Suspending or Stopping Overall Study
1243 1244 1245	In the case of an unanticipated system malfunction resulting in a severe hypoglycemia or severe hyperglycemia event (as defined in section 8.1.2.2), use of the study device system will be suspended while the problem is diagnosed.

D981-FF58-4975-AEFF PAGE 51 OF 74

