1515	 BG-measured hyperglycemic events (one BG record >350 mg/dL) 		
1516	 Worsening of HbA1c from baseline to 26 weeks by >0.5% 		
1517	• Other serious adverse events (SAE) and serious adverse device events (SADE)		
1518	• Adverse device effects (ADE)		
1519	 Unanticipated adverse device effects (UADE) 		
1520 1521	For the following outcomes, mean \pm SD or summary statistics appropriate to the distribution will be tabulated by treatment group:		
1522	• Number of SH events and SH event rate per 100 person-years		
1523	• Number of DKA events and DKA event rate per 100 person-years		
1524	• Any adverse event' rate per 100 person-years		

D981-FF58-4975-AEFF PAGE 62 OF 74

1525 1526 1527 1528	If enough events, the numbers will be compared between the two treatment arms using a robust Poisson regression. The regression will adjust for the participant-reported number of events prior to the start of the study and site as random effect. The amount of follow up will be included as an offset covariate to compare the rates.
1529 1530	Comparison of safety outcomes between the two treatment groups only include those events occurring on or after randomization until the 26 week visit.
1531 1532	Any pre-randomization adverse events will be tabulated separately and will include participants who were never randomized.
1533	10.9 Intervention Adherence
1534 1535	The following tabulations and analyses will be performed by treatment group to assess intervention adherence for the study:
1536	• Sensor use – hours of use and percent time of use
1537	• The daily frequency of downloaded BGM use
1538	For CLC arm only, the following will be tabulated to assess adherence:
1539	• % time in different operational modes per week - overall and by month
1540	10.10 Adherence and Retention Analyses
1541 1542	The following tabulations and analyses will be performed by treatment group to assess protocol adherence for the study:
1543 1544	 Number of protocol and procedural deviations per participant along with the number and percentage of participants with each number of deviations
1545	• Number of protocol and procedural deviations by severity with brief descriptions listed
1546 1547	• Flow chart accounting for all participants at all scheduled visits and phone contacts post treatment initiation to assess visit and phone completion rates
1548	 Number of and reasons for unscheduled visits and phone calls
1549	 Number of participants who stopped treatment and reasons

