## 200 201       5. Description of Statistical Methods

### 202 203       5.1. General Approach:

- 204       • All analyses comparing the CLC arm with SAP arm will follow the intention-to-treat  
 205       (ITT) principle with each participant analyzed according to the treatment assigned by  
 206       randomization.
- 207       • All randomized participants will be included in the primary and secondary analyses of  
 208       CGM metrics.
- 209       • All covariates obtained on a continuous scale will be entered into the models as  
 210       continuous variables, unless it is determined that a variable does not have a linear  
 211       relationship with the outcome. In such a case, categorization and/or transformation will  
 212       be explored.
- 213       • All p-values will be two-sided.
- 214       • Standard residual diagnostics will be performed for all analyses. If values are highly  
 215       skewed, then an alternate transformation, nonparametric, or MM estimation methods will  
 216       be used instead for the primary and secondary outcomes. Previous experience suggests  
 217       that no transformation, nonparametric, or MM estimation analyses will be necessary for  
 218       % time in range 70-180 mg/dL, % above 180 mg/dL, mean glucose, or HbA1c. Other  
 219       outcomes like % below 70 mg/dL over 26 weeks are skewed; however the differences  
 220       from baseline are expected to follow a normal distribution and there may be no need for  
 221       transformation, nonparametric, or MM estimation.

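### SAP section 8 triggers the severe hypoglycemia and DKA comparisons on 10 total events, with no rule for an arm that has none, where neither prescribed Wald p-value is valid

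*SAP*

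**What the plan says.** SAP section 8 lists severe hypoglycemia, DKA and any adverse event as numbers and rates per 100 person-years, then states the rule: "If there are at least 10 events across both treatment arms, the numbers will be compared between" the two arms by robust Poisson regression. Under the same trigger, the share of participants with an event is compared by logistic regression. Adjustment is for "participant-reported number of events 12 months prior to the start of the study and site as random" effect, with follow-up time as the offset. I read the threshold as applying to each outcome in turn.

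Protocol 10.8 leaves the threshold open: "If enough events, the numbers will be compared between the two treatment arms using a robust Poisson regression". SAP 5.1 adds "All p-values will be two-sided", and SAP 15 leaves safety p-values unadjusted for multiplicity.

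Repeat events in one person are foreseen. Protocol 8.5.1 lists among its reasons to discontinue the device "Two distinct severe hypoglycemia events as defined in section 8.1.2.1", with a parallel rule for DKA, and encourages the participant to stay in the study afterwards.

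Neither document sets a minimum number of participants with an event, a rule for an arm with no events or a small-sample correction. Neither says which of the two tests governs. The May 2019 SAP addendum does not touch this rule.

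**The concern.** Ten events need not mean ten participants, and the participant is the unit that was randomized. If a handful of people carry the events, 2:1 allocation makes it quite likely that all of them are in CLC. Both prescribed models then have no finite estimate of the treatment effect, yet software will usually still print a Wald p-value.

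These are the only prespecified between-arm tests of severe hypoglycemia and DKA in a pivotal device trial. Followed literally, the Poisson test can report overwhelming evidence of harm from a chance pattern. The logistic test can report no evidence at all when the imbalance is real.

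**Working it through.** **Inputs.** 168 randomized (SAP 3) at 2:1 (SAP 1) gives 112 CLC and 56 SAP. Tests are two-sided, and I take 0.05 as the nominal level. Follow-up is taken as equal. The documents give no expected event rate, clustering or error rate for these tests, so there is no stated figure to reproduce and the event patterns below are assumptions. The site random effect is not modelled.

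**1. Chance that all events fall in CLC.** If *k* participants carry the events and treatment has no effect, P = C(112,k)/C(168,k). This is 12.8%, 8.4%, 5.5%, 3.6% and 1.5% for k = 5, 6, 7, 8 and 10. The chance that all fall in SAP is far smaller (0.4% at k = 5), so these false signals point almost always at the device.

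**2. What the two tests return with an empty arm.** In a two-group Poisson model with event totals S1 and S0, the log rate ratio is ln[(S1/112)/(S0/56)]. Its robust variance is Σ(y−ȳ1)²/S1² + Σ(y−ȳ0)²/S0².

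Take 5 CLC participants with two events each and none in SAP. The CLC term is (20 − 10²/112)/10² = 0.191, so its square root is 0.437. The estimate diverges (the fit stopped at 22.1) while the standard error stays near 0.44, so p<0.0001. The logistic model separates: SE about 17,500, p=0.999.

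| Participants with an event, CLC vs SAP | Robust Poisson p | Logistic p | Fisher p |
|---|---|---|---|
| 5 (two events each) vs 0 | <0.0001 | 0.999 | 0.17 |
| 12 (one event each) vs 0 | <0.0001 | 0.999 | 0.009 |

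Neither Wald p-value responds to the evidence.

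**3. Null rejection by robust Poisson with exactly 10 events.** I enumerated every split of the event participants between arms, weighted each by its hypergeometric probability, and counted an empty arm as a rejection.

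| Who carries the 10 events | An arm is empty | Rejected, both arms with events | Total |
|---|---|---|---|
| 10 participants, one each | 1.5% | 1.7% | 3.2% |
| 8, at most two each | 3.6% | 3.3% | 6.9% |
| 7, at most two each | 5.5% | 2.8% | 8.3% |
| 6, at most two each | 8.5% | 1.0% | 9.5% |
| 5, two each | 13.1% | 0.0% | 13.1% |
| 5, as 5, 2, 1, 1, 1 | 13.1% | 7.3% | 20.4% |

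At 5 to 7 participants with at most two events each, most of the excess comes from empty arms.

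**4. Random event totals.** These runs simulate trials with an assumed mean of 10, 15 or 20 events and keep those with at least 10. Rejection is 3.5-4.0% for Poisson counts. For negative-binomial counts it is about 5% at shape 0.2, 6.2-7.0% at 0.1, 9.6-10.1% at 0.05 and about 19% at 0.02 (smaller shape means more clustering). Capping each person at two events (shapes 0.1 to 0.02, means 10 and 15) gives 4.4-6.9%.

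**The case against.** A reader might infer that the Poisson comparison has a false-positive rate of 8-14%. The documents do not support that as a general figure. It needs about 10 events concentrated in roughly 5 to 7 participants, or comparably strong clustering. With one event per person the test is conservative. The two-event rule in Protocol 8.5.1 would tend to limit repeats, although follow-up and event counting continue after the device is stopped. This part of the objection stands, and the size must be stated as conditional.

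A reader might also infer that the two tests contradict each other. An event rate and a percentage of participants are different quantities and may legitimately differ. The sound complaint is narrower: with an empty arm, neither p-value means anything.

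A statistician who sees a log rate ratio of 22 or a standard error of 17,500 would recognize non-estimation. That is fair, but the SAP says nothing about what to report then, and an improvised choice would be made with the data by arm in view.

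The planned model includes a site random effect that was not run here, so the printed p-values may differ in a mixed model. That limitation stands.

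Finally, no formal decision hangs on these tests. They lie outside the hierarchy, every reportable case is summarized, and under Protocol 8.6 the DSMB reviews each severe hypoglycemia and DKA event. This limits the consequence but does not make the p-values valid.

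**Conclusion.** The rule is deficient as written, in a limited way. It counts events rather than participants and has no provision for an arm without events. In that foreseeable case both Wald p-values are uninformative, in opposite directions. Null rejection by robust Poisson at exactly 10 events ranges from about 3% to about 20%, depending on a clustering pattern that the documents do not give. The figures assume 112:56, equal follow-up, no site effect and software that returns a p-value for an empty arm. If empty arms are not counted as rejections, the pattern of five participants with two events each falls from 13.1% to zero. The matter concerns the reading of severe hypoglycemia and DKA only.

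**What to change.** Issue a short SAP addendum to section 8:

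- Base the trigger on the number of participants with at least one event, not on events.
- Take the p-value for the percentage with an event from Fisher's exact test or Firth-penalized logistic regression.
- Take the p-value for the event rate from a permutation test with the participant as unit, permuting treatment within site to match the stratified randomization.
- When an arm has no events, report counts and an exact interval in place of the Wald results.

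Changing the trigger alone is not enough. Requiring at least 10 participants with an event lowers null rejection at shape 0.05 only from 9.6-10.1% to 7.0-9.4%, and the 12 versus 0 case would still pass.

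The choice of test should not depend on a minimum such as 3 participants per arm. That makes the method depend on the outcome by arm, and it would fail in 29% of null trials with ten one-event participants.

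The cost is a page of text and a few lines of code. The statistical price is conservatism with few events: with 5 participants the permutation p cannot fall below about 0.13 (12.8% + 0.4%). In addition, Fisher's test and the permutation test do not adjust for prior events.
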